11.7.3 Deaths and Serious Adverse Events

TEAEs that lead to death and SAEs will be summarized by SOC and PT. The following summaries will be presented for TEAEs leading to death and SAEs:

- Treatment-related treatment-emergent adverse events
- Sitravatinib-related treatment-emergent adverse events
- Nivolumab-related treatment-emergent adverse events
- Sitravatinib- or Nivolumab-related treatment-emergent adverse events
- Pembrolizumab-related treatment-emergent adverse events
- Enfortumab-related treatment-emergent adverse events
- Sitravatinib- or Pembrolizumab- or Enfortumab-related treatment-emergent adverse events

A listing of patients with TEAEs that led to death will be presented. A listing of patients who experience an SAE will also be presented.

11.7.4 Laboratory Data

All laboratory data will be summarized in International System (SI) units, with certain parameters (creatinine, BUN, bilirubin, phosphate, and calcium) repeated using British imperial units commonly used in the US. The conversion factors from conventional to SI units will be documented in the Local Lab Conventions document for this study. In general, laboratory data will be presented by visit.

Selected parameters will be presented in shift tables of baseline against worst grade test result. The shift from baseline to worst post baseline (including unscheduled visit) NCI CTCAE Version 5.0 grade will be presented by cohort and overall cohort combined for albumin (albumin increased), AST (AST increased), ALT (ALT increased), bilirubin (bilirubin increased), creatinine (creatinine increased), hemoglobin (anemia), neutrophils (neutrophil count decreased), platelets (platelet count decreased), sodium (hyponatremia and hypernatremia), potassium (hypokalemia and hyperkalemia), calcium (hypocalcemia and hypercalcemia), and uric acid (hyperuricemia).

For sodium, potassium, and calcium, separate grading criteria exist depending whether the analyte is high or low. For the purpose of shift tables, all low values will be included in the Grade 0 group in the shift tables for high values, and vice versa (all high values should be included in the Grade 0 group in the shift tables for low values).

Patients with at least 1 on-study measurement for each laboratory parameter will be included, regardless of whether or not a baseline assessment is present.

Clinical laboratory results will be listed by subject. Laboratory values that meet Grade 3 or 4 criteria according to NCI CTCAE Version 5.0 will also be listed separately.

Clinical laboratory parameters to be collected routinely on-study are listed in Table 10 below.

Table 10 Laboratory Safety Parameters

Hematology Panel	Blood Chemistry Panel
Hemoglobin	Aspartate aminotransferase (AST)
Platelet count	Alanine aminotransferase (ALT)
White blood cell count (WBC)	Alkaline phosphatase
Neutrophil count	Total bilirubin
Lymphocyte count	Direct bilirubin
	Indirect bilirubin
Coagulation	Lipase
International normalized ration (INR)	Amylase
Partial thromboplastin time (PTT)	Sodium
	Potassium
Urinalysis (dip stick)	Chloride
Blood	Bicarbonate [CO ²]
Protein	Blood urea nitrogen (BUN)
	Creatinine
Thyroid Function Test	Albumin
Thyroid stimulating hormone (TSH)	Total calcium
	Magnesium
	Uric acid
	Hemoglobin A1C (HgBA1c)

Pregnancy Testing: For patients of childbearing potential, a serum or urine pregnancy test will be performed by the local laboratory at screening. Pregnancy tests will also be done whenever pregnancy is suspected during the study.

11.7.4.1 Hematology

Hematology parameters include hemoglobin, platelet count, WBC count, lymphocytes, and neutrophils. The coagulation parameters include partial thromboplastin time (PTT), and international normalized ratio (INR).

Descriptive statistics will be provided for each test result and for change from baseline by cycle. Multiple measurements taken during the visit for a patient will be represented by the most severe value for each hematology test. The most severe value will be determined first by the value closest to the upper or lower limit of the normal limits (dependent on which direction is considered severe) if the value is within the normal limits. If the value is outside the normal limits, the value furthest from the upper or lower limit will be selected (dependent on which direction is considered severe). In the event that this algorithm does not allow for determining the most severe (e.g., a tie, etc.) the first chronological value will be selected. Low values are considered the most severe for all hematology parameters. Shift tables (for hemoglobin (anemia), neutrophils (neutrophil count decreased), platelets (platelet count decreased)), summarizing the shift from baseline grade to each post-baseline visit, maximum post-baseline CTCAE grade including unscheduled visits, and last assessment on study will be presented. Patients who develop a \geq Grade 3 toxicity will be listed.

11.7.4.2 Chemistry

Serum chemistry parameters include ALT, AST, alkaline phosphatase, total bilirubin, direct bilirubin, indirect bilirubin, lipase, amylase, creatinine, uric acid, BUN, albumin, sodium, potassium, chloride, magnesium, calcium and bicarbonate.

Descriptive statistics will be provided for each test result and for change from baseline by cycle. Multiple measurements taken during the visit for a patient will be represented by the most severe value as noted in Section 12.7.4.1. For all chemistry analytes, the most severe value is the highest value, with the exception of albumin, chloride, and bicarbonate. The most severe could be in either direction for potassium, sodium, and calcium. For these analytes, if within the normal limits, then the value closest to the normal limit (either direction) will be selected. If outside the normal limits, then the value most distant from the normal limit (either direction) will be used. Shift tables (for AST (AST increased), ALT (ALT increased), creatinine (creatinine increased), sodium (hyponatremia and hypernatremia), potassium (hypokalemia and hyperkalemia), and uric acid (hyperuricemia), summarizing the shift from baseline grade to each post-baseline visit, maximum post-baseline CTCAE grade including unscheduled visits, and last assessment on study will be presented. Patients who develop a \geq Grade 3 toxicity will be listed.

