The population PK analysis suggested that the following factors had no clinically important effect on the clearance of pembrolizumab: age (15 to 94 years), sex, race (89% White), renal impairment ($eGFR \geq 15$ mL/min/1.73 m²), mild hepatic impairment (total bilirubin [TB] less than or equal to the upper limit of normal [ULN] and AST greater than ULN or TB <1 to 1.5 times ULN or AST >ULN), or tumor burden. The impact of moderate or severe hepatic impairment on the PK of pembrolizumab is unknown.

1.5.3.2 **Pembrolizumab Anti-Drug Antibodies**

Of 1289 patients who were treated with KEYTRUDA as a single agent, at a dose of 2 mg/kg Q3W, 200 mg Q3W, or 10 mg/kg Q2W or Q3W and evaluable for the presence of anti-pembrolizumab antibodies, 2% tested positive for treatment-emergent anti-pembrolizumab antibodies by an electrochemiluminescent (ECL) assay of whom 0.5% had neutralizing antibodies against pembrolizumab. There was no evidence of an altered

pharmacokinetic profile or increased incidence of infusion reactions with anti-pembrolizumab binding antibody development.

1.5.3.3 *Pembrolizumab Adverse Reactions Common in Clinical Trials*

Refer to the current [KEYTRUDA US Prescribing Information](#) for information concerning adverse reactions occurring in clinical trials.

As of April 2020, the most common adverse reactions ($\geq 20\%$) in patients administered KEYTRUDA as a single agent were fatigue, musculoskeletal pain, decreased appetite, pruritus, diarrhea, nausea, rash, pyrexia, cough, dyspnea, constipation, pain, and abdominal pain.

As of April 2020, the most common adverse reactions ($\geq 20\%$) in patients administered KEYTRUDA in combination with chemotherapy were fatigue/asthenia, nausea, constipation, diarrhea, decreased appetite, rash, vomiting, cough, dyspnea, pyrexia, alopecia, peripheral neuropathy, mucosal inflammation, and stomatitis.

As of April 2020, the most common adverse reactions ($\geq 20\%$) in patients administered KEYTRUDA in combination with lenvatinib were fatigue, hypertension, musculoskeletal pain, diarrhea, decreased appetite, hypothyroidism, nausea, stomatitis, vomiting, decreased weight, abdominal pain, headache, constipation, urinary tract infection, dysphonia, hemorrhagic events, hypomagnesemia, PPE, dyspnea, cough, and rash.

1.5.3.4 *Pembrolizumab Immune-Mediated Adverse Events*

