11.7.4.5 CTCAE Coding of Laboratory Data

Where laboratory values are categorized into NCI CTCAE Version 5.0 grades, the categories are defined according to the criteria available on the following website: <http://evs.nci.nih.gov/ftp1/CTCAE/About.html>.

Note that grades are applied based only on the numeric SI value of the parameter assessed; clinical signs and symptoms are not considered. Where categories are only distinguished by clinical signs or symptoms, the lowest of the possible grades will be assigned.

NCI CTCAE grades will be applied for the following lab parameters:

- Hematology: hemoglobin, WBC, lymphocyte, neutrophils, and platelets.
- Chemistry: ALT, albumin, Alkaline phosphatase, AST, total bilirubin, calcium, creatinine, magnesium, potassium, sodium, uric acid.

Laboratory measurements that are within their institutional limits of normal and are not graded as 1-4, per the CTCAE, will be summarized as "Grade 0," which is defined as normal.

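### SAP 11.7.4.2 leaves magnesium out of the either-direction analytes, so a low magnesium with a higher repeat at the same visit drops out of the by-cycle statistics

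*SAP*

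**What the plan says.** SAP 11.7.4.2 (Chemistry) names magnesium among the serum chemistry parameters, in the run "albumin, sodium, potassium, chloride, magnesium, calcium and bicarbonate". It plans descriptive statistics by cycle for each result and for change from baseline. Where a visit has more than one measurement, one most severe value represents the patient. The directions are set by two sentences:

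- The default, with its exceptions: "For all chemistry analytes, the most severe value is the highest value, with the exception of albumin, chloride, and bicarbonate".
- The group treated as two-sided, which does not name magnesium: "The most severe could be in either direction for potassium, sodium, and calcium".

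SAP 11.7.4.5 includes magnesium among the CTCAE-graded analytes ("total bilirubin, calcium, creatinine, magnesium, potassium, sodium, uric acid"). The shift tables listed in SAP 11.7.4 and 11.7.4.2 do not include it.

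SAP 11.7.4.1 (Hematology) sets the parallel rule for blood counts: "Low values are considered the most severe for all hematology parameters". It defines that group as follows: "Hematology parameters include hemoglobin, platelet count, WBC count, lymphocytes, and neutrophils". It then names PTT and INR separately, as coagulation parameters.

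**The concern.** Magnesium can be abnormal in either direction, like the three electrolytes that the SAP does treat as two-sided. The general chemistry rule protects only the high side.

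The sequence most exposed is a low result, replacement, and a normal recheck recorded at the same visit. That sequence is foreseeable, because Protocol 5.5.1.1 gives electrolyte supplementation as an example of routine supportive care. The rule would carry the corrected value into the by-cycle table and leave the low one out.

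Because no magnesium shift table is planned, the by-cycle statistics are the only magnesium-specific summary that the SAP describes. At stake is whether that table can show low magnesium at visits with repeats.

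**Working it through.** The plan states no figure on this point, so there is nothing to reproduce. The check has three parts: reading the rule, applying it to assumed values, and seeing what else captures a low result.

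**1. Where magnesium falls (SAP 11.7.4.2)**

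| Group | Analytes named | Value kept |
|---|---|---|
| Exceptions to highest | albumin, chloride, bicarbonate | not the highest; low is implied |
| Either direction | potassium, sodium, calcium | the most distant from the limits, if any is outside them |
| All others | includes magnesium | highest |

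Magnesium is in neither named group, so the default applies.

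**2. The rule applied**

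The limits and results below are assumptions for illustration. The documents give none. Assume magnesium limits of 0.70 to 1.05 mmol/L.

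- Results 0.80 and 0.45. Current rule: max(0.80, 0.45) = 0.80. Either-direction rule: only 0.45 is outside the limits, by 0.70 − 0.45 = 0.25, so 0.45 is kept.
- Results 0.90 and 1.40. Current rule: max(0.90, 1.40) = 1.40. Either-direction rule: only 1.40 is outside, by 1.40 − 1.05 = 0.35, so 1.40 is kept.

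The two rules differ only in the first case, so the gap is on the low side alone.

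In that case the recorded value is 0.80 − 0.45 = 0.35 mmol/L too high for that patient and visit. In a cohort of 40, the maximum for Cohorts 1 to 4, with all 40 contributing at that cycle, one such patient moves the mean by 0.35 / 40 = 0.00875 mmol/L. The mean would barely change. The tabulated minimum is where the loss could show.

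**3. What else would capture a low result**

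- Protocol 8.2.1: an abnormal result is reported as an adverse event if, among other triggers, it needs treatment or intervention. A replaced magnesium meets this.
- SAP 11.7.4: all laboratory results are listed by subject, and Grade 3 or 4 values are also listed separately. Magnesium is graded, so it is covered.
- SAP 11.7.4.2: patients with chemistry toxicity of Grade 3 or higher are listed.
- Shift tables: none for magnesium.

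A Grade 1 or 2 low value that meets no trigger in Protocol 8.2.1 appears only in the by-subject listing.

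**4. INR and PTT (SAP 11.7.4.1)**

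The low-is-severe sentence covers hematology parameters. The section defines these as five tests and names INR and PTT outside them. Read literally, no direction is set.

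With assumed INR limits of 0.8 to 1.2 and results of 1.0 and 2.8, a low rule would keep 1.0 and a high rule 2.8. With assumed PTT limits of 25 to 37 s and results of 30 and 70, a low rule would keep 30 and a high rule 70. The choice matters, but the SAP does not make it.

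**The case against.** The strongest case against the point is that little is lost. The example that causes worry, a low magnesium that is replaced, must be reported as an adverse event and so reaches the treatment-emergent tables whatever value the visit rule selects. Every result is listed, and Grade 3 or 4 values are listed again. Chemistry is scheduled once per visit (Protocol Tables 1 and 3), so repeats within a visit are not routine. All of this stands, and it limits the point to the by-cycle statistics.

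The evidence that low magnesium is expected here is also thin. The protocol names it in a list ending "hemorrhagic events, hypomagnesemia, PPE, dyspnea, cough, and rash" (section 1.5.3.3), which describes pembrolizumab with lenvatinib, a regimen not used in this study. Pembrolizumab is given only in Cohort 9, whose lead-in may enrol up to 30 patients; the note to SAP Figure 1 says that the Cohort 9 expansion and Cohort 10 will not open. The protocol's lists of common reactions for sitravatinib alone or with nivolumab, for nivolumab, and for enfortumab with pembrolizumab do not name hypomagnesemia.

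A reader might infer that the SAP selects the lowest INR and PTT, because both sit under the Hematology heading. The text does not support that: it calls them coagulation parameters and applies the low rule to the other group. The upper INR limit in inclusion criterion 7h, for Cohorts 9 and 10 only, suggests that high is the direction of concern. That supports stating a direction; it does not show that the wrong one was chosen.

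None of this puts magnesium into either named group, so the gap in 11.7.4.2 remains.

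**Conclusion.** The point holds as a minor drafting gap. Followed exactly, SAP 11.7.4.2 keeps the highest magnesium at a visit and drops a low one from the by-cycle descriptive statistics, with no magnesium shift table to offset this. The conclusion rests on the SAP wording alone; the numerical examples only illustrate it.

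Three stronger readings should be avoided.

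- The rule does not run backwards for magnesium. High values are still kept, and only the low side is unprotected.
- It does not affect every visit with more than one result. It matters only where a low value would have been selected under the either-direction rule.
- It does not make the safety reporting as a whole understate hypomagnesemia. Adverse event tables and laboratory listings are unaffected.

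The frequency is unknown, because the documents do not say how often magnesium is repeated within a visit. No efficacy analysis, cohort decision or dose-escalation rule depends on this value.

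**What to change.** In SAP 11.7.4.2, add magnesium to the analytes that may be severe in either direction, so that the existing procedure for potassium, sodium and calcium applies to it.

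Two small clarifications can go into the same edit:

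- In SAP 11.7.4.1, state that the highest value is the most severe for INR and PTT.
- In SAP 11.7.4.2, correct the cross-reference to Section 12.7.4.1. Section 12.0 is the reference list, and the selection rule is in 11.7.4.1.

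The cost is one added word, one sentence, one corrected section number and a change to the programming lookup table. No new data are needed. SAP 5.0 already provides for an amended SAP before database lock.

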11.7.4.3 Urinalysis

Urinalysis results for the parameters blood and protein will be listed.

11.7.4.4 Thyroid

Results will be listed for Thyroid stimulating hormone (TSH).

11.7.4.5 CTCAE Coding of Laboratory Data

Where laboratory values are categorized into NCI CTCAE Version 5.0 grades, the categories are defined according to the criteria available on the following website: <http://evs.nci.nih.gov/ftp1/CTCAE/About.html>.

Note that grades are applied based only on the numeric SI value of the parameter assessed; clinical signs and symptoms are not considered. Where categories are only distinguished by clinical signs or symptoms, the lowest of the possible grades will be assigned.

NCI CTCAE grades will be applied for the following lab parameters:

- Hematology: hemoglobin, WBC, lymphocyte, neutrophils, and platelets.
- Chemistry: ALT, albumin, Alkaline phosphatase, AST, total bilirubin, calcium, creatinine, magnesium, potassium, sodium, uric acid.

Laboratory measurements that are within their institutional limits of normal and are not graded as 1-4, per the CTCAE, will be summarized as "Grade 0," which is defined as normal.

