DLTs with single-agent administration of sitravatinib in Study 516-001 included Grade 3 PPE at 80 mg, and intolerable Grade 2 neuropathy, intolerable Grade 2 fatigue, and intolerable Grade 2 mucositis at 200 mg. In Study MRTX-500, there were no DLTs observed during the lead-in evaluation of the combination of nivolumab (240 mg IV Q2W) and sitravatinib (120 mg QD).

Sitravatinib-related adverse events (AEs) reported in $\geq 20\%$ of 186 patients in sitravatinib monotherapy studies were diarrhea (50%), fatigue (42%), hypertension (39%), nausea

(29%), decreased appetite (27%), vomiting (24%), and palmar-plantar erythrodysesthesia (20%). Treatment-related Grade 3+ AEs reported in $\geq 5\%$ of patients were hypertension (19%), diarrhea (10%), fatigue (7%), lipase increased (5%), and PPE (5%).

Treatment-related Grade 4 AEs were reported in 3 patients and included lipase increased in 2 patients (1%) and febrile neutropenia in 1 patient (1%). A treatment-related Grade 5 AE of cardiac arrest was reported in 1 patient (1%).

Treatment-related AEs reported in $\geq 20\%$ of 184 patients treated with sitravatinib in combination with nivolumab were diarrhea (50%), fatigue (46%), nausea (34%), decreased appetite (33%), hypertension (27%), weight decreased (26%), dysphonia (24%), vomiting (23%), and hypothyroidism (20%). Treatment-related Grade 3 AEs reported in $\geq 5\%$ of patients were hypertension (19%), diarrhea (10%), fatigue (7%), and lipase increased (5%). Treatment-related Grade 4 AEs were reported in 4 patients (2%) overall, and included gastric ulcer perforation, hypertensive crisis, lipase increased, and lymphocyte count decreased in 1 patient each (1%). Treatment-related Grade 5 AEs of cardiac arrest were reported in 2 patients (1%).

In particular, treatment-related AEs reported in $\geq 20\%$ of 40 patients treated with sitravatinib in combination with nivolumab in Study 516-003 as of 26 June 2019 (enrolled mostly in Cohorts 1 through 4) were fatigue (58%), diarrhea (55%), decreased appetite (38%), dysphonia (38%), nausea (30%), lipase increased (28%), alanine aminotransferase increased (25%), PPE (25%), hypertension (20%), dysgeusia (20%), vomiting (20%), and proteinuria (20%). Treatment-related Grade 3 AEs reported in $\geq 5\%$ of patients were hypertension (20%), diarrhea (10%), fatigue (10%), lipase increased (10%), and PPE (5%). No treatment-related Grade 4 or Grade 5 AEs were reported.

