Increased lipase has been observed in patients treated with sitravatinib and other inhibitors of the VEGF pathway. Although the mechanism has not been fully elucidated, inhibition of VEGF may lead to acinar cell apoptosis resulting in the release of autodigestive enzymes (Sevin-2012). Most sitravatinib treatment-emergent events of increased amylase and lipase were asymptomatic while some were associated with signs and/or symptoms of pancreatitis. Treatment-related increased lipase has been observed in 10% of patients treated with sitravatinib monotherapy. Increased lipase is rare with pembrolizumab monotherapy, however it occurs in 18% (8/45) of urothelial carcinoma patients receiving the combination of pembrolizumab and enfortumab in Study EV-103 (Rosenberg-2020).

Finally, whereas sitravatinib administered in combination pembrolizumab and enfortumab is unlikely to result in drug-drug interactions (DDI), the only potential for DDIs stems from MMAE being an in vitro substrate of both CYP3A4 and P-glycoprotein (P-gp) (see below), and sitravatinib being an in vitro inhibitor of both CYP3A4 and P-gp (see Section 1.7.1.2). To mitigate the potential for increased MMAE exposure with the combination of sitravatinib, pembrolizumab and enfortumab and any subsequent clinical impact, the lead-in dose escalation evaluation (Cohort 9) of the combination will initiate with a sitravatinib starting dose representing three dose levels (~65%) below the dose administered as a single-agent and in combination with nivolumab in Phase 2 and Phase 3 trials. In addition, a dose de-escalation step for enfortumab may be undertaken as appropriate. Refer to [Appendix 9](#) for study design details of cohorts investigating the combination of sitravatinib, pembrolizumab and enfortumab.

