5.5 Management of Adverse Events

5.5.1 Sitravatinib-Related Adverse Events

5.5.1.1 General Management of Non-Hematological Toxicities

In the event of symptomatic sitravatinib-related AEs, dose reduction to a level that can be administered continuously is preferred over continuing dosing until interruption becomes necessary. Symptomatic Grade 2 sitravatinib-related non-hematological AEs occurring any time on study, particularly early in treatment (e.g., Cycle 1 Day 15 or Cycle 2 Day 1), are recommended to be managed using dose reduction to the next lower dose level, per the reduction schedule outlined in [Table 5](#) (free base capsule formulation) and [Table 6](#) (malate capsule formulation), rather than treatment interruption.

Non-hematological toxicities \geq Grade 3 and considered to be related to sitravatinib treatment should be managed with sitravatinib interruption, with or without dose reduction, until resolution of toxicity to \leq Grade 1 or to baseline value. If the toxicity is adequately managed by routine supportive care (such as electrolyte supplementation), or is a Grade 3 amylase or lipase elevation, treatment may be resumed at the same dose; if not, treatment may be resumed at a reduced dose as outlined in [Table 8](#). Recurrence of the toxicity may be managed similarly. If sitravatinib is interrupted for \geq 28 days, permanent discontinuation of sitravatinib should be considered.

Table 8: Sitravatinib Dose Modifications – Non-Hematological Drug-Related Toxicities¹

Toxicity	Treatment Delay	Dose Modification
Grade 1	Continue treatment unchanged	
Grade 2 Asymptomatic	May be implemented based on Investigator discretion ²	
Grade 2 Symptomatic	May be implemented based on Investigator discretion ² Dose reduction to the next lower dose level is recommended over treatment interruption	
Grade 3 or 4	Hold until \leq Grade 1 or return to baseline ²	Resume at dose level one or more levels below that inducing the toxicity. Exceptions presented in footnotes ^{2,3}

¹ Management of adverse events of interest for sitravatinib are presented in Section 5.5.1.3.

² The current [OPDIVO US Prescribing Information](#), [KEYTRUDA US Prescribing Information](#) and [PADCEV US Prescribing Information](#) must be consulted to determine appropriate dose modifications for nivolumab, pembrolizumab and enfortumab.

³ Patients may resume at the same dose in the following cases:

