- Grade 3 or 4 electrolyte abnormality that is not clinically complicated and resolves spontaneously or with conventional medical treatment within 72 hours;
- Grade 3 or 4 amylase or lipase elevation that is not associated with symptoms or clinical manifestations of pancreatitis.

5.5.1.2 *General Management of Hematological Toxicities*

Hematological toxicities are not a frequent cause of treatment interruption or discontinuation of sitravatinib treatment. Observed \geq Grade 3 hematological events that are considered to be causally related to sitravatinib should initially be managed using treatment interruption. In addition, dose reduction of sitravatinib should be implemented in the following cases:

- Grade 3 or 4 febrile neutropenia;
- Grade 4 neutropenia persisting for \geq 8 days; or
- Grade 4 thrombocytopenia of any duration or Grade 3 thrombocytopenia with bleeding.

5.5.1.3 *Management of Selected Adverse Event*

The following are guidelines for management of potential adverse events more specific to treatment with sitravatinib or agents in the same class of cancer treatment.

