8.2.1 Laboratory Abnormalities

An abnormal laboratory test result should be reported as an AE in the CRF only if it is associated with one or more of the following:

- Clinical symptoms;
- Requires additional tests (beyond repeats), treatment or intervention;
- Results in change in study treatment dosing;
- Requires discontinuation from study treatment; and/or
- Considered by the Investigator or Sponsor to be an AE.

Hy's Law

Hepatic function abnormality defined by an increase in AST and/or ALT to $\geq 3 \times$ ULN concurrent with an increase in total bilirubin to $\geq 2 \times$ ULN but without increase in alkaline phosphatase (i.e., alkaline phosphatase $< 2 \times$ ULN) meets the criteria for Hy's Law and raises the concern for drug-induced liver injury when no other cause of the abnormal laboratory results is identified. Follow-up investigations and inquiries will be initiated promptly by the investigational site to determine whether the findings are reproducible and/or whether there is objective evidence that clearly supports causation by a disease (e.g., cholelithiasis and bile duct obstruction with distended gallbladder) or an agent other than study treatment(s).

Cases meeting Hy's Law should be reported as SAEs. Study treatments (sitravatinib, nivolumab, *or* sitravatinib, pembrolizumab and enfortumab) should be permanently discontinued for a Hy's Law case.

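### SAP 11.7.4.5 leaves lipase and amylase off its closed list of CTCAE-graded tests, and the albumin shift table in 11.7.4 is labelled in the opposite direction to 11.7.4.2

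*SAP*

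**What the plan says.** SAP 11.7.4.5 says which tests receive a CTCAE v5.0 grade. It names five hematology tests and then "Chemistry: ALT, albumin, Alkaline phosphatase, AST, total bilirubin, calcium, creatinine, magnesium, potassium, sodium, uric acid". The list has no wording that leaves it open. Grades rest on the numeric value alone; where categories differ only by signs or symptoms, the lowest possible grade is used.

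SAP 11.7.4.2 gives descriptive statistics by cycle for a longer chemistry list that does contain both tests: "Serum chemistry parameters include ALT, AST, alkaline phosphatase, total bilirubin, direct bilirubin, indirect bilirubin, lipase, amylase" and ten more. It adds that patients with toxicity of Grade 3 or above will be listed. SAP 11.7.4 likewise plans a separate listing of Grade 3 or 4 values. Neither sentence restricts the tests. Protocol 9.5.3 plans both a listing and a summary of Grade 3 or 4 values, again without restriction.

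The protocol refers to these two tests by grade when it discusses resuming sitravatinib. Section 5.5.1.1 has "or is a Grade 3 amylase or lipase elevation, treatment may be resumed at the same dose", and footnote 3 to Table 8 has "Grade 3 or 4 amylase or lipase elevation that is not associated with symptoms or clinical manifestations of pancreatitis".

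On albumin, SAP 11.7.4 labels the shift table as an increase. SAP 11.7.4.2 treats the highest value as most severe for chemistry tests but excepts albumin.

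**The concern.** Severity of laboratory abnormalities is part of the secondary safety endpoint (Protocol 2.2.2), and lipase is a known signal here. Protocol 1.3.3.2 reports increased lipase as a treatment-related AE in 28% of 40 patients in this study, with Grade 3 in 10%. Protocol 1.7.2.2 adds: "Most sitravatinib treatment-emergent events of increased amylase and lipase were asymptomatic while some were associated with signs and/or symptoms of pancreatitis".

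Asymptomatic laboratory findings are the ones that AE tables can miss. Under Protocol 8.2.1 an abnormal result "should be reported as an AE in the CRF only if it is associated with one or more of the following", and a list of conditions follows. A graded laboratory table counts values without that filter. A programmer who follows 11.7.4.5 as written would not produce one for lipase or amylase.

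For albumin, a shift table built on the label would show rises and not falls, although the SAP's own severity rule points to falls.

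**Working it through.** No sample size or error rate is involved. The check compares the lists and then traces what reaches the AE tables.

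**1. Graded against collected chemistry tests**
- 11.7.4.2 names 18 tests: ALT, AST, alkaline phosphatase, total, direct and indirect bilirubin, lipase, amylase, creatinine, uric acid, BUN, albumin, sodium, potassium, chloride, magnesium, calcium, bicarbonate.
- 11.7.4.5 grades 11 of them.
- 18 − 11 = 7 ungraded: lipase, amylase, BUN, chloride, bicarbonate, direct bilirubin, indirect bilirubin.
- Of the seven, only lipase and amylase are individually named by grade in the protocol. The other five are not at issue.

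**2. The signal in this study** (Protocol 1.3.3.2, data to 26 June 2019)
- Any grade: 28% of 40; 11/40 = 27.5%, so 11 patients.
- Grade 3: 10% of 40 = 4 patients.
- These are AE rates. They show that lipase matters and that many events are already captured as AEs. They do not estimate what is missed.

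**3. What the AE tables already hold**
- Protocol 5.5.1.1 and Table 8 call for a sitravatinib hold for related non-hematological toxicity of Grade 3 or 4.
- The lipase and amylase exceptions concern the dose at resumption. They do not remove the hold.
- Protocol 8.2.1 counts a change in study treatment dosing among its AE conditions, and also the judgement of the Investigator or Sponsor.
- A sitravatinib-related Grade 3 or 4 value managed per protocol therefore normally becomes an AE.
- The remainder is mainly values judged unrelated, values after dosing ends (chemistry is also drawn at the End of Treatment visit) and cases where no hold occurred. The documents give no count for any of these.

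**4. Albumin and the shift-table lists**
- Chemistry tests with shift tables in 11.7.4: albumin, AST, ALT, bilirubin, creatinine, sodium, potassium, calcium, uric acid = 9.
- In 11.7.4.2: AST, ALT, creatinine, sodium, potassium, uric acid = 6.
- 9 − 6 = 3 missing from 11.7.4.2: albumin, bilirubin, calcium. Both sections plan a shift to the worst post-baseline grade, so the lists overlap in purpose and should agree.
- If high albumin is not the severe direction, low is. Protocol 4.1 agrees: its albumin criterion for Cohorts 9 and 10 is a floor of 2.5 g/dL.

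**5. Glucose**
- Protocol Table 11 includes glucose for Cohorts 9 and 10. It is the only Table 11 chemistry test named in neither SAP Table 10 nor 11.7.4.2.

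**The case against.** The strongest reply is that little is lost. Lipase and amylase keep descriptive statistics, patient listings and AE tables, and step 3 shows that most related high-grade values should reach those tables. That stands, and it is why the point is minor. A reader might infer that the SAP hides the lipase signal; the documents do not support that.

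A second reply is that the omission is not a settled exclusion, because the listing sentences in 11.7.4 and 11.7.4.2 can be read as covering every test with a CTCAE grade. This also stands. It shows an ambiguity between sections, which still needs resolving before programming.

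Third, Protocol section 9 allows the SAP to modify protocol plans, so narrowing 9.5.3 is permitted. True, but nothing in the SAP says that this narrowing is intended.

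Fourth, the albumin label may be a slip. Grades come from the CTCAE criteria rather than from a label, and the rule that puts opposite-direction values in Grade 0 covers only sodium, potassium and calcium. Albumin is also on the graded list, so values of Grade 3 or above would still be listed. The contradiction is real, but low albumin is lost from the shift table only if the label is programmed as written.

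Two further readings are tempting and do not hold:
- **Cohort 9 glucose has no planned summary.** SAP Table 3 footnote 7 points to Protocol Table 11. The 11.7.4.2 list is introduced as what chemistry parameters include, with statistics for each result, and 11.7.4 speaks of summarising all laboratory data. Glucose is unnamed, which does not establish that it is unsummarised. The protocol's pre-dose glucose criterion for enfortumab is an administration check and does not oblige the SAP to tabulate against it.
- **WBC, lymphocytes, alkaline phosphatase and magnesium are a defect because they are graded without a shift table.** Protocol 9.5.3 plans shift tables for selected parameters only, and Grade 3 or 4 values of these four are listed. Having no count for them is a small departure that Protocol section 9 permits.

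**Conclusion.** The point holds as a minor inconsistency in the laboratory safety outputs. Read literally, 11.7.4.5 gives lipase and amylase no laboratory grade, so they enter no graded output. That conflicts with Protocol 9.5.3 and with the SAP's own listing sentences. It affects 2 of 18 chemistry tests. The albumin label contradicts 11.7.4.2 for one test.

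The number of Grade 3 or 4 lipase or amylase values absent from the AE tables cannot be derived. That it is limited rests on two assumptions: that related values are managed with the hold the protocol describes, and that sites treat a hold as a dosing change under 8.2.1. The CTCAE text is not in the documents, so how many values would reach Grade 3 or 4 under the SAP's numeric-only, lowest-grade rule cannot be checked either. ORR, the AE tables and the DLT rules are unaffected.

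**What to change.** Amend the SAP before database lock:
- Add lipase and amylase to the graded list in 11.7.4.5, under the numeric-value rule already there. Include them in the Grade 3-4 listing and in a Grade 3-4 count.
- Change the albumin shift table in 11.7.4 to the low direction.
- Use one shift-table list in 11.7.4 and 11.7.4.2, which adds albumin, bilirubin and calcium to the latter.
- As a small reconciliation, name Cohort 9 glucose in SAP Table 10 and 11.7.4.2 to match Protocol Table 11.

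The cost is a few added or relabelled rows in existing tables and programs. No new data are collected.
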